8.5.5 Collection of Mandatory Samples for Biomarker Analysis

- Samples for biomarker research are required and will be collected from all participants in this study as specified in the SOA ([Table 1](#) and [Table 2](#)).
- Samples include the following:
 - Nasal mucosal sampling. Nasal mucosa (for mRNA) is collected using a sterile, disposable nasal mucosal collection device to curette a sample of nasal mucosa for analysis.
 - Nasal mucosal lining fluid. Nasal mucosal lining fluid is collected using the Nasosorption™ FX·i device, which is gently applied to the nasal mucosa to absorb mucosal lining fluid from mucosal surfaces.
 - Whole blood for RNA PAXgene. RNA PAXgene will be used for the collection, transport, and storage of whole blood, and the stabilization of intracellular RNA. RNA transcript profiling analyses will be performed on RNA PAXgene samples.

Note: If nasal mucosal sampling for mRNA at SV4 (randomisation) is deemed by the investigator to have been challenging for individual participant tolerability (eg, due to nasal polyps), subsequent nasal sampling may be omitted at the investigator's discretion.

Biological samples will be collected at specified visits as detailed in the SOA ([Table 1](#) and [Table 2](#)):

- Total IgE (serum).
- Allergen-specific IgE (serum).
- EDN (plasma).
- sST2 (serum).

- Exploratory serum biomarkers, including but not limited to:
 - CCI [REDACTED]
 - IL-5 (serum).
 - IL-13 (serum).
 - TSLP (serum).
- IL-33 isoforms (nasal lining fluid).
- mRNA transcriptome (blood and nasal mucosal sample).
- Pharmacogenetic sampling (blood):
 - CCI [REDACTED]
 - [REDACTED]
 - CCI [REDACTED]
 - CCI [REDACTED]

For storage, re-use and destruction of human biological samples, see [Appendix C](#).

8.5.6 Other study related biomarker research

Already collected samples may be analysed on different biomarkers thought to play a role in asthma including, but not limited to, serum analytes, or tissue biomarkers and/or specific candidate genes/genome-wide analysis for RNA, to evaluate their association with observed clinical responses to MEDI3506.

For storage, re-use and destruction of biomarker samples, see Section [Appendix C](#).

8.6 Optional Genomics Initiative Sample

Collection of optional samples for genomics initiative research is also part of this study as specified in the SOA ([Table 1](#) and [Table 2](#)) and is subject to agreement in the ICF.

A blood sample for this genetic research will be obtained from the participants at SV4. Although DNA is stable, early sample collection is preferred to avoid introducing bias through excluding participants who may withdraw due to an AE. If for any reason the sample is not

drawn at SV4, it may be taken at any visit until the last study visit. Only one sample should be collected per participant for genetics during the study.

For storage and destruction of genetic samples, see [Appendix D](#).

8.7 Health Economics

Not applicable.

8.8 Impact of COVID-19 Pandemic

To assess the impact of the COVID-19 pandemic on the study, sites will be asked to complete the pandemic impact form at each study visit, according to the SOA ([Table 1](#) and [Table 2](#)).

9 STATISTICAL CONSIDERATIONS

9.1 Statistical Hypotheses

The primary efficacy endpoint is the change from baseline in pre-BD FEV₁ at Week 16. A treatment policy estimand will be applied whereby all available data are included in the analysis, irrespective of whether a participant discontinued study intervention or received rescue therapy.

The null hypothesis is that the change from baseline in FEV₁ at Week 16 for participants dosed with MEDI3506 is equal to the change from baseline in FEV₁ at Week 16 for participants dosed with placebo. The alternative hypothesis is that the change from baseline in FEV₁ at Week 16 for participants dosed with MEDI3506 is greater than the change from baseline in FEV₁ at Week 16 for participants dosed with placebo, ie:

- H0: Change from Baseline in FEV₁ at Week 16 (MEDI3506-placebo) = 0.
- H1: Change from Baseline in FEV₁ at Week 16 (MEDI3506-placebo) > 0.

Hypothesis testing will be performed at the one-sided 10% level. If the p-value is < 0.1, reject H0 and accept H1. A hierarchical testing strategy will be used to preserve the type I error for the comparisons of each of the 2 dose levels of MEDI3506 versus placebo, as follows:

- Step 1: Test MEDI3506 600 mg versus placebo in regard to H0
- Step 2: If previous step rejects: test MEDI3506 300 mg versus placebo in regard to H0

9.2 Sample Size Determination

A sample size of 216 participants (72 participants per treatment group), randomised 1:1:1 to MEDI3506 **CCI** mg: MEDI3506 **CCI** mg: placebo, will provide at least 80% power to detect a statistically significant difference in change from baseline to Week 16 in pre-BD FEV₁,

assuming a difference of 150 mL between placebo and MEDI3506, a between-participant SD of 420 mL and a one-sided- 10% alpha level. To allow for 5% participants being ineligible for the primary analysis, a total of approximately 228 participants will be randomised (approximately 76/arm).

Up to 60 participants are intended to be included in the cough sub-study (ie, approximately 20 participants per treatment group). However, given the exploratory nature of the sub-study and that it may not be activated in all countries, randomisation of participants not included in the sub-study will not be restricted, therefore, sub-study recruitment may not be achieved. Since limited data are available on cough monitoring in this population, the sub-study is considered exploratory and no formal power calculations have been performed.

9.3 Populations for Analyses

The following populations are defined:

Table 8 Populations for Analysis

Population/Analysis set	Description
ITT population	Participants who are randomised and receive any study intervention. Participants will be analysed according to their randomised treatment group.
As-treated Population	Participants who are randomised and receive any study intervention. Participants will be analysed according to the treatment they actually receive.
PK population	Participants who received at least one dose of MEDI3506 and had at least one detectable serum concentration measurement post first dose of study intervention. Participants will be analysed according to the treatment they actually receive.

ITT = Intent-to-treat; PK = pharmacokinetic(s).

The ITT population will be used to summarise all demographic and baseline characteristics, concomitant medications, and efficacy measures. The As-treated population will be used to summarise all safety measures (AEs, laboratory tests, ECG, and vital signs). The PK population will be used to summarise PK measures.

9.4 Statistical Analyses

All personnel involved with the analysis of the study will remain blinded until Primary clinical data lock and until Clinical Study Protocol deviations are identified.

Analyses will be performed by AstraZeneca or its representatives. A comprehensive SAP will be developed and finalised before Primary clinical data lock and will describe the participant populations to be included in the analyses, and procedures for accounting for missing, unused, and spurious data.

This section is a summary of the planned statistical analyses of the primary and secondary endpoints. Any deviations from this plan will be reported in the CSR.

9.4.1 General Considerations

Efficacy analyses will be performed using the ITT population.

The primary estimand is a ‘Treatment Policy’ estimand, as follows: The difference in mean change from baseline in FEV₁ at Week 16 (MEDI3506 – placebo) will be estimated using a repeated measures mixed effects analysis of covariance model, for the ITT population. This will include all available data from all visits up to and including Week 16, irrespective of whether the participant discontinued study intervention or received rescue therapy.

Demography and baseline characteristics will be summarised by treatment group for the ITT population.

9.4.2 Efficacy

9.4.2.1 Primary Endpoint

The difference in mean change from baseline in FEV₁ at Week 16 (MEDI3506 – placebo) will be estimated using a repeated measures mixed effects analysis of covariance model, for the ITT population. The model will include all available data from all visits up to and including Week 16, irrespective of whether the participant discontinued study intervention or received rescue therapy. No imputation will be made for missing data, as a repeated measures model is being applied. The model will include fixed effects for baseline, visit, treatment and the baseline by visit and treatment by visit interactions.

The significance of the treatment effect will be tested at a 10% one-sided level of significance as described in Section 9.1.

9.4.2.2 Secondary and Exploratory Endpoints

Change from baseline in ACQ-6, SGRQ and AO parameters will be analysed using a repeated measures analysis of covariance model, similar to that described for the primary efficacy analysis (Section 9.4.2.1). PRO responder endpoints at Week 16 will be analysed using a chi-squared test.

Objective cough measurements will be analysed using analysis of covariance, and may be log-transformed prior to analysis. Estimates of the least square mean change from baseline for each treatment, and the difference between them, together with 80% confidence interval and one-sided p-values, will be obtained from the model for each visit.

Time to first CompEx event and time to first asthma exacerbation will be analysed using a Cox proportional hazard model, with treatment fitted as a covariate. The data will also be displayed in a Kaplan-Meier plot. The CompEx event rate will be analysed using negative

binomial regression, with the log(follow-up time) included as an offset term. The dependent variable will be the number of CompEx events through Week 16, and the model will include treatment group as a fixed effect. All available data from participants through to Week 16 will be included, irrespective of whether they discontinued study intervention.

Change from baseline to Week 16 in concentration of FeNO will be analysed using a repeated measures analysis of covariance model, similar to that described for the primary efficacy analysis (Section 9.4.2.1). Where appropriate, endpoints may be log-transformed prior to analysis. Estimates of the least square mean change from baseline for each treatment, and the difference between them, together with 80% confidence interval and one-sided p-values, will be obtained from the model for each visit.

The difference in mean change from baseline in post-BD FEV₁, and the change in FEV₁ % reversibility at Weeks 8 and 16 will be estimated using a repeated measures mixed effects analysis of covariance model, similar to that described for the primary efficacy analysis (Section 9.4.2.1).

The composite estimand will be the difference between MEDI3506 and placebo response rate at Week 16 in the ITT population. Participants with missing data at Week 16 will be considered non-responders. For each MEDI3506 group compared with placebo, the odds ratio and 80%, and one-sided p-values will be reported.

9.4.3 Subgroup Analyses

Subgroup analyses may be performed and will be described in the SAP.

9.4.4 Safety

The occurrence of AEs and SAE will be described by System Organ Class, Preferred Term, severity, and relationship to the study intervention. Participants will be counted only once for each preferred term, once for each system organ class, and by the highest severity of an event. Number of participants with elevated liver function tests that meet the HL definition will be evaluated. Laboratory evaluations will be summarised with descriptive statistics at each visit and change from baseline summarised for each post-baseline visit. Laboratory measurements will also be summarised based on the number and percentage of participants above or below a pre-specified threshold for each test. The number of participants with clinically significant abnormal ECG results based on investigators' judgments will be summarised at each visit. Change from baseline in vital signs will be summarised by visit.

9.4.5 Other Analyses

9.4.5.1 Immunogenicity and PK

Positive antibodies to MEDI3506 will be reported by treatment group. If there is a high incidence of ADA, the association of ADA with MEDI3506 concentration will be assessed. In

addition, the relationship between ADA and biomarkers, efficacy, and safety may be evaluated. MEDI3506 serum concentrations will be tabulated along with descriptive statistics. Mean and individual serum MEDI3506 concentration-time profiles will be plotted. Population PK modelling may be performed if data allow, but will not be reported in the CSR. The potential correlation between PK exposure and biomarkers, and efficacy/safety response may be evaluated.

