3.4.2.1 ADA definitions

ADA detection at sample level:

- A sample is considered to be ADA positive if the titre is greater than or equal to the minimum required dilution (MRD) of the assay.
- A sample is considered to be ADA negative if the titre is <MRD of the assay.

ADA detection at participant level:

- A participant is considered ADA positive if at least one collected sample is tested positive at any time during the study, including baseline and/or post-baseline (see definition for ADA prevalence in Section 3.4.2.2).
- A participant is considered ADA negative if collected samples are tested negative at all timepoints, including baseline and post-baseline.

Subjects with a missing baseline ADA assessment should be assumed to be ADA negative as a conservative approach to ensure that all subjects are included in all analyses.

Treatment-related ADA development at participant level:

Treatment-emergent ADA positive (TE-ADA+) is defined as being either of treatment-induced ADA positive (ADA negative at baseline and at least one post-baseline ADA positive) and treatment-boosted ADA positive (ADA positive at baseline and baseline titre is boosted by greater than the variability of the assay (ie ≥ 4 -fold increase) at ≥ 1 post-baseline timepoint). Treatment-emergent ADA negative (TE-ADA-) is defined as ADA positive but not fulfilling the definition of TE-ADA positive.

The median of maximum titres is calculated based on the maximum titre for each ADA positive participant within each treatment group (including baseline and post-baseline measurements).

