4.2.8 Other analysis

4.2.8.1 Immunogenicity and PK

Summary of ADA responses during the study with number and percentage of participants in each category (defined in Section 3.4.2.2) and ADA titres over time displaying min, Q1, median, Q3 and max, will be provided by treatment group. The impact of ADA on MEDI3506 PK concentrations will be assessed. Summary of AEs by ADA status will be provided. The relationship between ADA and biomarkers or efficacy might be evaluated.

MEDI3506 serum concentrations will be tabulated along with descriptive statistics.

Geometric mean (together with gSD) serum MEDI3506 concentration over time will be plotted by treatment. Individual serum MEDI3506 concentration over time plots will be provided. Spaghetti plots of individual serum MEDI3506 concentrations over time by ADA category (TE-ADA negative, TE-ADA positive, ADA negative) will also be generated.

All serum concentrations data will be listed for PK population. ADA results and participants key subject information for ADA positive participants will be provided for the As-treated population.

Separately from the CSR, population PK modelling may be performed and reported, and potential correlation between PK exposure and pharmacodynamic biomarker, efficacy/safety response may be evaluated.

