14.2 Exploratory cough sub-study		
Table 14.2.17.1	Objective cough measures over time, summary statistics	Exploratory cough sub-study population
Table 14.2.17.2	Percent and relative change from baseline to Week 16 in objective cough measures treatment comparisons, ANCOVA	Exploratory cough sub-study population
Table 14.2.18.1	Cough VAS by visit, summary statistics	Exploratory cough sub-study population
Table 14.2.18.2	Change from baseline to Week 16 in cough VAS treatment comparisons, ANCOVA	Exploratory cough sub-study population
PK Outputs		
Table 14.2.19.1	Summary of serum concentration (ug/L) of MEDI3506 by treatment	PK population
Table 14.2.19.2	Summary of serum concentrations (ug/L) of MEDI3506 over time by Anti-Drug Antibody category	PK population
Figure 14.2.19.1	Geometric mean (gSD) serum concentrations (ug/L) of MEDI3506 versus time by treatment (Linear scale)	PK population

Figure 14.2.19.2	Individual serum concentrations (ug/L) of MEDI3506 versus time by treatment (Linear scale)	PK population
Figure 14.2.19.3	Individual serum concentrations (ug/L) time profile of MEDI3506 by Anti-Drug Antibody category - spaghetti plot	PK population
Immunogenicity		
Table 14.2.20.1	Summary of Anti-Drug Antibody responses during the study	As-treated population
Table 14.2.20.2	Anti-Drug Antibody results and titre summary by timepoint	As-treated population
Table 14.2.20.3	Pre-BD FEV1 (as measured in the clinic) at Week 16 by Anti-Drug Antibody category, summary statistics	As-treated population
Table 14.2.20.4	Pre-BD FEV1 (as measured in the clinic) at Week 24 by Anti-Drug Antibody category, summary statistics	As-treated population
Table 14.2.20.5	Adverse events during the treatment and follow-up periods in any category by Anti-Drug Antibody category	As-treated population
Table 14.2.20.6	Number of subjects with adverse events by system organ class and preferred term by Anti-Drug Antibody category	As-treated population

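### ADA status is built from all samples to Week 24 but is used to group Week 16 FEV1, earlier drug levels and earlier AEs, so these descriptive contrasts can be biased in either direction

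*Protocol*

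**What the plan says.** Protocol 9.4.5.1 sets only the aim: "the relationship between ADA and biomarkers, efficacy, and safety may be evaluated". The classification is in SAP 3.4.2.1. A participant is positive if "at least one collected sample is tested positive at any time during the study", and the opposite category is equally open-ended: "A participant is considered ADA negative if collected samples are tested negative at all timepoints, including baseline and post-baseline". Treatment-induced positivity needs only "ADA negative at baseline and at least one post-baseline ADA positive". Under SAP 3.4.2.2, a baseline-negative participant whose last available sample is positive is even classed as persistently positive.

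SAP 3.4.2 schedules ADA samples at SV4, SV6 to SV10, SV12 and early discontinuation, that is, at Weeks 0, 1, 4, 8, 12, 16 and 24. One scheduled sample therefore falls after Week 16.

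SAP 4.2.8.1 commits to assessing the impact of ADA on drug concentrations and states "Summary of AEs by ADA status will be provided". It leaves the relation to efficacy optional. Appendix C nevertheless lists, as Table 14.2.20.3, "Pre-BD FEV1 (as measured in the clinic) at Week 16 by Anti-Drug Antibody category, summary statistics" and, as Table 14.2.20.5, "Adverse events during the treatment and follow-up periods in any category by Anti-Drug Antibody category". Table 14.2.20.6 gives AEs by system organ class and preferred term within ADA category, and Table 14.2.19.2 gives concentrations over time by ADA category. Neither document limits ADA status to samples taken by the time of the outcome or lets it vary over time.

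**The concern.** A grouping variable that includes results obtained after the outcome is hard to interpret as a cause of that outcome. A participant negative at every visit through Week 16 and first positive at Week 24 sits in the ADA-positive column for FEV1 measured eight weeks earlier, for every earlier serum concentration, and for AEs that began before any antibody was seen.

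Immunogenicity is a secondary objective. A reader of the study report will use these tables to judge whether antibodies lower exposure, blunt efficacy or bring AEs. If the groups mix people with and without detected ADA at the time of the outcome, an apparent absence of an ADA effect is weak reassurance, and an apparent effect may come from the grouping.

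**Working it through.** **1. The plan's own figures.** The documents give no ADA incidence, no share of late converters and no drug tolerance for the assay, so there is no ADA figure to reproduce. The illustrations below borrow the SD of 420 mL and 72 per arm from Protocol 9.2. Those figures reproduce: 2 × (1.2816 + 0.8416)² × (420/150)² = 70.7, so 71 per arm against the stated 72, and 72 per arm gives 80.5% power at one-sided 10%.

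**2. One participant traced through the rules.** Baseline negative, negative at Weeks 1 to 16, first positive at SV12 (scheduled Day 169). SAP 3.4.2.1 makes this participant ADA positive and treatment-emergent positive; SAP 3.4.2.2 adds persistently positive if that is the last sample. The label then applies to FEV1 at Day 113, which is 169 − 113 = 56 days earlier. The Week 24 FEV1 table (14.2.20.4) does not have this problem for a Week 24 positive.

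**3. Week 16 FEV1.** Let D be the true difference from never-positives in those positive by Week 16, q the share of the ADA-positive group first positive later, and c the Week 16 difference of those late converters from never-positives. Then

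observed contrast = (1 − q) × D + q × c.

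Take D = -150 mL, an assumption chosen only for scale:

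| q | c = 0 | c = -150 mL | c = -250 mL |
|---|---|---|---|
| 0.10 | -135 | -150 | -160 |
| 0.25 | -112 | -150 | -175 |
| 0.50 | -75 | -150 | -200 |

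The contrast shrinks if late converters looked like negatives, is unbiased if they already had the same deficit, and is inflated if their deficit was larger.

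**4. What classification to date would do.** With c = 0 it recovers -150 mL. The cost is precision. Assume 20% incidence among 2 × 72 = 144 active participants, so 28.8 positives and 115.2 negatives. The SE is 420 × √(1/28.8 + 1/115.2) = 88 mL for the whole-study grouping, and 91, 98 or 117 mL for status to date at q = 0.10, 0.25 or 0.50.

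If the late converters really had masked ADA with the same effect (c = -150 mL) and q = 0.50, then 14.4 of the 129.6 participants counted as not yet positive are misplaced. Status to date then gives -150 + (14.4/129.6) × 150 = -133 mL, while the whole-study grouping gives -150 mL. Neither version is always the better one.

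**5. Concentrations.** On the log scale with c = 0, an assumed true trough ratio of 0.60 would appear as exp((1 − q) × ln 0.60), which is 0.66, 0.72 or 0.77 for q = 0.20, 0.35 or 0.50. Masking matters here. Protocol 5.3 equates 16 weeks with 5 half-lives, so one half-life is 3.2 weeks. SAP 3.5.2 shows SV9 (Week 12) as the last dosing visit. With simple exponential decline, 0.5^(4/3.2) = 42% of the level remains at Week 16 and 0.5^(12/3.2) = 7% at Week 24. If the assay is drug-sensitive, a first positive at Week 24 may be an antibody that was there earlier.

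**6. AEs.** A simulation assumed seroconversion uniform in time reaching 20% by Week 24, a 50% background AE risk over 24 weeks, ADA tests at Weeks 1, 4, 8, 12, 16 and 24, and 5% to 20% withdrawal. Between 30% and 33% of positives were first detected at Week 24.

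- With a true hazard ratio of 2 after seroconversion, the whole-study grouping gave a rate ratio of about 1.40, and 57% to 58% of first AEs in positives came before the first positive sample.
- With no ADA effect, positives still showed more AEs: 49.7% against 48.7% at 5% withdrawal, and 48.7% against 44.9% at 20%. Staying longer in the study allows both more AEs and more ADA tests.

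**The case against.** The tables are descriptive, outside the primary test, and carry no decision rule; reporting AEs by ADA status records co-occurrence and attributes nothing. Only one scheduled sample falls after Week 16. All of this stands and limits the weight of the point.

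Four stronger readings might be inferred, and the documents support none of them.

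- *Any ADA effect is necessarily diluted.* That needs late converters to resemble negatives at Week 16. The arithmetic shows inflation is also possible, and ADA masked by drug could make a Week 24 positive a true earlier positive. Protocol 8.5.3 leaves assay details to a separate report, so the direction is not known.
- *These tables are the only check on ADA impact.* Table 14.2.20.2 gives ADA results and titres by time point, individual concentration plots are planned, and Appendices 16.2.6.4 to 16.2.6.6 and 16.2.7.2 list concentrations, ADA results, ADA-positive participants and their AEs. The sequence can be reconstructed person by person, though no planned summary does so.
- *The Week 16 table will change between the two locks.* It could if it is produced at the primary analysis, when only earlier enrollees have a Week 24 sample. SAP 4.1 refers possible cut-off rules to a separate document, and nothing says these tables are run at that lock.
- *The same three categories apply in every table.* SAP 4.2.8.1 names treatment-emergent positive, treatment-emergent negative and ADA negative only for the spaghetti plots. Their use elsewhere is a reasonable inference. The point does not depend on it, since every participant-level category in SAP 3.4.2 that separates positive from negative after baseline uses the whole study.

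**Conclusion.** The point holds as a matter of classification. The SAP's ADA status uses samples up to Week 24, and the planned tables apply it to outcomes measured earlier. That follows from the text without any assumed figure. The fault lies in SAP 3.4.2.1, 3.4.2.2 and 4.2.8.1 and Appendix C; Protocol 9.4.5.1 states only an intention.

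The resulting bias can run either way, and its size cannot be stated. The figures of -75 to -200 mL, 0.66 to 0.77 and 1.40 rest on assumed values of D, q, c, incidence, trough ratio and hazard ratio, and serve only to show that the effect need not be trivial. Replacing the whole-study grouping outright is not supported either, because with masked ADA it could be the more accurate one. The effect is confined to interpretation of immunogenicity; the primary FEV1 test and the sample size are untouched. This is a cheap improvement to the planned outputs.

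**What to change.** Keep the any-time definition for ADA prevalence and incidence, and keep the whole-study tables. In SAP 4.2.8.1 and Appendix C, add:

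1. A version of Table 14.2.20.3 that classifies by ADA samples dated up to the Week 16 spirometry. Use dates rather than analysis visits: in SAP 3.1.4 the Week 16 immunogenicity window runs to Day 141, while the spirometry window ends at Day 127.
2. Concentrations by ADA status to date, alongside Table 14.2.19.2, with the first positive sample marked on the individual concentration plots.
3. In Tables 14.2.20.5 and 14.2.20.6, AEs with onset before and on or after the first positive sample shown separately, with person-time denominators. Never-positive participants contribute all their time to the period without detected ADA, so they need no index date.

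The cost is SAP wording and programming; no new samples are needed. There are two downsides. ADA-positive groups are smaller at earlier time points, and along the concentration profile group membership changes. Status to date may also miss ADA masked by circulating drug, which is why both versions should be shown.
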